### **Exploratory efficacy endpoints:**

For both vaccine groups, the following proportions will be estimated with an exact 95% CI within the PP set

- Proportion of subjects taking antibiotics due to a post-influenza (qRT-PCR- or culture-confirmed) respiratory tract infection,
- Proportion of subjects hospitalized due to an ILI, with or without confirmation by viral culture or qRT-PCR analysis.
- Proportion of subjects who died due to an ILI, with or without confirmation by viral culture or qRT-PCR analysis.
- Proportion of subjects with serious ILI with or without confirmation by viral culture or qRT-PCR analysis
- Proportion of subjects taking medications due to qRT-PCR- or culture-confirmed ILI

Between-groups comparisons will be performed using the Fisher's exact test.

For both vaccine groups, if the number of subjects having more than 1 hospitalization is at least 10, in addition to the analysis defined above, the rate of hospitalizations associated with ILI episodes over the flu season and its 95% CI will be estimated for the PP set by means of a Poisson model, applied on the number of events with duration of follow-up as offset. The event rate (/year) will be estimated in each group (a year being defined as 365 days).

In addition, the following descriptive statistics will be provided to describe the ILI episodes:

- For the PP set, the distribution of influenza confirmed episodes

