5.3. Treatment Assignment Procedures

5.3.1. Randomization Procedures

Central randomization will be implemented in this study. Subjects will be randomized to 1 of 2 treatment arms, based on a computer-generated randomization schedule prepared by or under the supervision of the sponsor before the study. The randomization will be stratified by cohort and age group (i.e., 50- 65, ≥ 65) and balanced by using permuted blocks. At least 50% of study participants will be 65 or older in each randomization cohort. The Interactive Web Response System (IWRS) will assign a unique treatment code, which will dictate the treatment assignment and matching study drug kit(s) for the subject.

For season 2, the randomization will be further stratified by sub-study participation (i.e. Yes or No).

For the CMI substudy, 350 subjects from sites participating to the sub-study (sub-study sites) are randomly chosen among 700 sub-study sites subjects with approximately 263 subjects selected at random from 350 M-001 sub-study sites subjects and approximately 87 from 350 placebo sub-study sites subjects.

Once consented and upon entry of demographic data and confirmation of eligibility for this trial, the subject will be enrolled. A total of 12,000 subjects will be randomly assigned to one of 2 arms: experimental and control. A total of 700 subjects will be randomly chosen to participate to the sub-study, with approximately 263 subjects selected at random from 350 M-001 sub-study sites subjects and approximately 87 from 350 placebo sub-study sites subjects.

The investigator will not be provided with randomization codes. The codes will be maintained within the IWRS, which has the functionality to allow the investigator to break the blind for an individual subject, if necessary.

Per International Conference on Harmonisation (ICH) guideline E6: Good Clinical Practice (GCP), screening records will be kept at each participating site to document the reason why an individual was screened, but failed trial entry criteria.

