11.5.1. Analysis Populations

The Safety Analysis population includes all subjects who received at least one dose of study vaccine. Subjects in the safety population will be analyzed according to the treatment actually received.

The intent-to-treat (ITT) population includes all subjects who received at least one dose of study vaccine. Subjects in the ITT population will be analyzed according to their randomization.

The per protocol (PP) population includes all subjects in the ITT subset satisfying the following criteria:

- Subject met all protocol-specified inclusion criteria and met no exclusion criterion,
- Subject received both doses of M-001/placebo as randomized, in the protocol-specified time frame, and at the intended dose level,
- Subject did not receive M-001/placebo that was not properly handled or was otherwise not acceptable for administration,
- Subject had at least one successful surveillance contact 15 days or more after the second dose of M-001/placebo, or attended at least one ILI visit due to ILI symptoms
- Subject did not receive a seasonal influenza vaccine between randomization and end of the surveillance period for Season 1,
- Subject did not receive a licensed live vaccine within 30 days of any dose of M-001/placebo, and
- Subject did not receive a licensed non-live vaccine within 21 days of any dose of M-001/placebo.

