14.9. Disclosure of Individual Research Information

In this protocol, it is not planned to provide each participant with a summary of overall study results as these will be generally published by the sponsor. The sponsor will register and/or disclose the existence of and the results of clinical studies as required by international and local regulations. Disclosure of assignment to study arms for individual subjects can be provided during the study only based on justified urgent medical need as assessed by the sponsor, and after the study has been completed, as per local regulations and based on sponsor's decision.

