#### **Per-Protocol (PP) Set**

The primary efficacy analysis set (PP Set) will exclude

- Subjects who did not satisfy all protocol-specified inclusion criteria or met at least one exclusion criterion,
- Subjects who did not receive both doses of M-001/placebo as randomized,
- Subjects who did not receive M-001/placebo that was properly handled or was otherwise not acceptable for administration (unblinded subjects will be excluded),
- Subjects or their representative who were not contacted by the surveillance center, did not have any phone call, or any visit 15 days or more after second injection,

- Subjects who received a seasonal influenza vaccine between randomization and end of the surveillance period,
- Subjects who received a licensed live vaccine within 30 days of any dose of M-001/placebo that interfered with the evaluation of the investigational product, and
- Subjects who received a licensed non-live vaccine within 21 days of any dose of M-001/placebo that interfered with the evaluation of the investigational product.

Data from the database will be used to flag the protocol violations.

The results of the NP or nasal and throat swab collected outside of the allowed window following the ILI will be considered valid.

List of subjects excluded from the per-protocol analysis will be finalized prior to unblinding the database and described in the blinded data analysis memo.

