Table 14.2.23.6	Protocol Defined ILI During Flu Season – Poisson Analysis - Per-Protocol Population – Per-Protocol Population	
Table 14.2.23.7	Proportion of Subjects with Protocol Defined ILI During Flu Season – Descriptive Statistics - Overall, By Season, By Age Group – ITT Population	
Table 14.2.23.8	Proportion of Subjects with Protocol Defined ILI During Flu Season – Analysis - Overall, By Season, By Age Group – ITT Population	
Table 14.2.23.9	Protocol Defined ILI During Flu Season – Poisson Analysis - Per-Protocol Population – ITT Population	
Table 14.2.24.1	Proportion of subjects with Antibiotics Intake Post-Influenza – Per-Protocol Population	
Table 14.2.24.2	Death Due to ILI – Per-Protocol Population	x
Table 14.2.24.3	Proportion of subjects with hospitalization associated with Flu Season ILI – Descriptive Statistics – Overall, By Season, By Age Group – Per-Protocol Population	
Table 14.2.24.4	Proportion of subjects with hospitalization associated with Flu Season ILI– Analysis - Per-Protocol Population	x
Table 14.2.24.5	Rate of hospitalization associated with Flu Season ILI episodes– Poisson Analysis - Per-Protocol Population	
Table 14.2.24.6	Proportion of subjects with serious ILI – Per-Protocol Population	x
Table 14.2.24.7	Proportion of subjects taking medications due to qRT-PCR- or culture-confirmed ILI – Per-Protocol Population	x

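### Hospitalised, serious and fatal ILI are compared only in the per-protocol set, and the SAP's undeclared exclusion of unblinded subjects could drop a severe case from its own endpoint

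*SAP*

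**What the plan says.** SAP 5.4.2, on the exploratory efficacy endpoints: "For both vaccine groups, the following proportions will be estimated with an exact 95% CI within the PP set". The list that follows includes hospitalisation, death and serious illness due to ILI, each compared between arms by Fisher's exact test. Appendix 1 agrees: Tables 14.2.24.2 to 14.2.24.6 are all PP, for example "Death Due to ILI – Per-Protocol Population" and "Proportion of subjects with serious ILI – Per-Protocol Population". Protocol 11.5.3 already places deaths and the hospitalisation rate on the PP set; the SAP added serious ILI as an endpoint. In contrast, SAP 5.4.2 supports the primary analysis with an ITT analysis and runs all secondary efficacy assessments on both sets.

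The SAP's PP definition (5.3) excludes "Subjects who did not receive M-001/placebo that was properly handled or was otherwise not acceptable for administration (unblinded subjects will be excluded"). The matching criterion in Protocol 11.5.1 reads "Subject did not receive M-001/placebo that was not properly handled or was otherwise not acceptable for administration" and says nothing about unblinding. SAP section 11, which lists departures from the protocol, does not mention the addition. The SAP's opening change summary says only that the PP exclusion criteria were clarified.

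On individual unblinding, Protocol 14.9 says that disclosure of the study arm "can be provided during the study only based on justified urgent medical need as assessed by the sponsor". Protocol 5.3.1 describes a web response system "which has the functionality to allow the investigator to break the blind for an individual subject, if necessary". Protocol 9.5 lets the DSMB ask for one subject's arm for safety assessment. Operating rules are left to a separate Unblinding Plan (Protocol 5.3.2).

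**The concern.** Two choices combine. First, the rarest and clinically heaviest efficacy outcomes have no analysis in the set that keeps subjects as randomised, so there is nothing against which to check the PP comparison. Second, membership of the PP set can depend on what happens to a subject after dosing. If a code is broken because the subject is seriously ill, and the illness is an ILI, the exclusion is triggered by the event being counted. That subject then leaves both numerator and denominator of the severe endpoint and, if influenza is confirmed, the primary PP case count too. Fixing the exclusion list before the database is unblinded gives no protection, because the individual code break has already taken place.

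Protocol 11.5.3 expects very few hospitalisations, so each lost event weighs heavily. If the loss differs between arms, the randomised comparison is distorted.

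**Working it through.** **The plan's own figure.** Only the primary endpoint has a design calculation: 182 cases, 80% power, null vaccine efficacy (VE) 40%, true VE 62% (SAP 3.4). With equal arms, the probability that a case is in the vaccine arm is 0.6/1.6 = 0.375 under the null and 0.38/1.38 = 0.2754 under the alternative. With 182 cases, the exact lower limit exceeds 40% if at most 55 are vaccine cases; the power is 81.5%. Expected cases, reading 2.41% as the placebo rate: 12,000 × 0.9 / 2 × 0.0241 × 1.38 = 179.6. The plan's figure reproduces. No figure is stated for the severe endpoints.

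**Severe endpoints.** The documents give neither a hospitalised-ILI rate nor an unblinding frequency, so what follows rests on assumptions: 5,400 PP subjects per arm (12,000 × 0.9 / 2), placebo risk 0.1% to 0.5%, VE 62%, and a share f of hospitalised cases lost through code breaks.

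- No loss: expected cases (vaccine/placebo) are 5,400 × 0.001 × 0.38 = 2.1 and 5,400 × 0.001 = 5.4 at 0.1% risk; 10.3 and 27.0 at 0.5%.
- Equal loss: both counts are multiplied by (1 − f), so VE stays at 62% and only precision suffers. At 0.5% risk, on rounded counts:

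| f in both arms | Vaccine / placebo cases | Fisher p |
|---|---|---|
| 0 | 10 / 27 | 0.008 |
| 10% | 9 / 24 | 0.013 |
| 25% | 8 / 20 | 0.036 |
| 50% | 5 / 14 | 0.063 |

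- Unequal loss: apparent VE = 1 − 0.38 × (1 − f_V)/(1 − f_P). With f_V = 25% and f_P = 50% it is 1 − 0.38 × 0.75/0.50 = 43%; reversed, 1 − 0.38 × 0.50/0.75 = 75%.

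**PP restriction without any code break.** The planned 10% loss is 1,200 of 12,000 subjects. On the same assumptions, the whole trial would yield 6,000 × 0.001 × 1.38 = 8.3 to 6,000 × 0.005 × 1.38 = 41.4 hospitalised cases, and a tenth of these is 0.8 to 4.1. This is an upper bound on what an ITT table recovers, since Protocol 11.3.3 counts in that 10% subjects lost to follow-up or without data, whose events may never be captured.

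**Primary PP result.** Start from 50 against 132 cases with 5,400 per arm; the cases removed are an assumption.

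| Vaccine / placebo cases | VE | Exact lower 95% limit |
|---|---|---|
| 50 / 132 | 62.1% | 47.2% |
| 50 / 129 (placebo only) | 61.2% | 45.9% |
| 50 / 127 (placebo only) | 60.6% | 45.0% |
| 49 / 129 (near-proportional) | 62.0% | 46.8% |
| 48 / 127 (near-proportional) | 62.2% | 46.9% |

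About 15 placebo-only removals are needed before the limit reaches 40%. At the boundary one case can decide: 55 against 127 gives 40.1%, and 55 against 126 gives 39.6%.

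**The case against.** A reader might infer that the rule does delete the severe events. The documents do not support this. Nothing in them says that a hospitalised, serious or fatal ILI leads to a code break, no frequency of unblinding is given, and the Unblinding Plan is not available. If no ILI case is unblinded, the exclusion removes nothing.

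The scope of the added words is also uncertain. They stand inside the product-handling criterion: "otherwise not acceptable for administration (unblinded subjects will be excluded"). In a trial where the two products look different and a staff member prepares the syringe unblinded, the phrase may mean only unblinding through handling or administration. A DSMB request answered in closed session need not make anyone an unblinded subject for this purpose.

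The events are not lost from the report. Protocol 9.2.4 has serious ILI recorded as a serious adverse event in parallel, SAP 4.3 and 4.4 tabulate these in the Safety Population, and Appendix 1 lists all ILIs for the ITT set. The primary VE analysis is repeated on ITT, so a divergence from PP would be visible. The endpoints are exploratory, and SAP 10.1 treats everything beyond the primary endpoint as supportive. The placebo-only example is one-sided: near-proportional removal barely moves the limit.

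All of this stands, and it limits the point. It does not remove it. The serious adverse event tables are organised by MedDRA term and do not compare hospitalised or fatal ILI between arms, and a listing is not an analysis. The ambiguity of the parenthesis is a reason to settle its scope, because it sits in the definition of the primary analysis set.

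**Conclusion.** The point holds in a limited form. Three facts are textual: the severe ILI endpoints have no ITT counterpart, in either the SAP or the protocol; the SAP's PP definition carries an unblinding exclusion that the protocol lacks and section 11 omits; and individual code breaks are tied to urgent medical need. Together they allow, on a literal reading, selection that depends on the outcome. Its size cannot be derived from the documents. It is zero if no severe case is unblinded, a loss of precision if the shares are equal across arms, and a bias in either direction if they are not. The illustrative figures rest on the assumed 0.1% to 0.5% risk, VE of 62% and assumed shares lost.

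A reader might go further and conclude that the primary result is compromised. That is not supported: the ITT primary analysis retains these subjects, and in the worked example even five placebo-only removals leave the lower limit at 45.0%. This is an inexpensive improvement to the plan.

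**What to change.** - SAP 5.4.2 and Appendix 1: add ITT analyses of hospitalised, serious and fatal ILI alongside the PP tables. SAP 5.1 already sets the onset rule for one-dose subjects, so no new definition is needed.
- SAP 5.3: give the unblinding exclusion its own criterion and limit it, so that a code break after case counting begins (14 days after dose 2) removes neither a case nor a member of the denominator.
- SAP section 11: declare the exclusion as a change from Protocol 11.5.1.
- SAP 8.1: report the number of unblinded subjects by arm, so that readers can see whether the issue arose.

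The cost is a few extra tables from data already held, plus SAP wording. One drawback remains: what a subject reports after a code break is no longer blind, though events up to that date are unaffected. No change to unblinding practice or clinical management is proposed.

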## **6. IMMUNOGENICITY ENDPOINTS**

A subset of subjects was enrolled in Season 2 to assess immunogenicity.

The endpoint for assessing the immune response is the change from baseline in the percentage of CD4+ lymphocytes producing Th1 cytokine (e.g. INF- $\gamma$ ) in response to any of the 9 peptides in M-001 measured at  $14 \pm 2$  days after the day of the second vaccination.

Immunogenicity analyses will be detailed in a separate SAP.

## **7. SUBGROUP ANALYSES**

### **7.1 Vaccine-by-Subgroup Interaction**

To assess the consistency of the vaccine efficacy across different subgroups, Breslow-Day test for the homogeneity of the odds ratios will be used; this analysis will be performed on the PP population.

The following subgroups will be tested:

- Cohort : 1 and 2, corresponding to season 2018-2019 and 2019-2020
- Age: <65 years and  $\geq 65$  years overall and by age within each cohort
- Gender: M and F : overall and by sex within each cohort
- Flu Type (A, B)

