11.5.3. Analysis of Efficacy Data

Primary Efficacy Assessment

For the primary analysis of vaccine efficacy (VE), the efficacy of M-001 after a first influenza season in each cohort will be estimated by

$$VE = 1 - [(C_V / N_V) / (C_P / N_P)]$$

where C_V and C_P are the number of per protocol cases of influenza meeting the primary case definition in the vaccine and placebo group, respectively, and N_V and N_P are the number of per protocol subjects in the vaccine and placebo group, respectively. The confidence interval for VE will be calculated by the Clopper-Pearson exact method conditional on the total number of cases in the vaccine and placebo groups combined. Similarly, vaccine efficacy and its 95% confidence interval will be calculated for the ITT population.

VE and its 95% confidence interval will be estimated by age group (i.e., < 65 years, ≥ 65 years) for both the PP and ITT analysis populations. Given VE for a specific age group can be approximated

by 1 minus the age group specific odds ratio, the Breslow-Day test for the homogeneity of the odds ratios will be used to test for a common VE across age groups. In addition, given that circulating strains of flu may vary over the course of the trial, VE and its 95% confidence interval will be estimated by flu season as well for both the PP and ITT analysis populations; Breslow-Day test for the homogeneity of the odds ratios will be used to test for a common VE across cohort (flu season).

If the study discontinuation or loss to follow-up rate varies by vaccine group, a Cox proportional hazards model will be used to estimate vaccine efficacy. For this analysis, time from 15 days after the second dose of study vaccine or placebo to the first episode of culture or PCR confirmed influenza caused by any influenza A or B virus in association with a protocol-defined influenza like illness (ILI) will be the endpoint. All subjects will be censored at the earliest of their date of study withdrawal, date of lost to follow-up, or end of their first influenza season defined as April 30th for countries in the northern hemisphere. The model will have a single covariate for vaccine group and will be stratified by age group. Vaccine efficacy will be estimated by 1 minus the estimated hazard ratio from this model. If the lower limit of the 95% confidence interval for vaccine efficacy based on the PP population is above 40%, the vaccine will have demonstrated sufficient efficacy.

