### 3.4 Study Design

This is a pivotal, multicenter, randomized, modified double-blind, placebo-controlled phase 3 trial to assess the safety and clinical efficacy of M-001, an influenza vaccine administered intramuscularly twice (2 doses 21 to 30 days apart) in older adults and the elderly ( $\geq 50$  years of age) who meet all eligibility criteria.

The study sample size of 12,000 subjects is based on the lower bound of the two-sided 95% confidence interval for vaccine efficacy (VE) being above 40% with 80% probability when true VE is 62%. It assumes 1:1 randomization, a 2.41% attack rate in the study population, and no more than 10% of subjects lost to follow-up or excluded from the per protocol population. Under these assumptions, 182 first episodes of qRT-PCR-confirmed influenza of any strain occurring at least 15 days after the second dose of study vaccine or control and prior to the end of the first influenza season will be needed to demonstrate efficacy is at least 40%.

A total of up to 10 sites are selected to participate to the Cell Mediated Immunity (CMI) substudy. A total of 350 subjects are randomly chosen among 700 subjects from the selected sites: approximately 263 subjects selected at random from 350 M-001 subjects and approximately 87 from 350 placebo subjects; placebo subjects being selected to maintain the study blind. Assuming that among the 263 M-001 selected subjects, 210 will have valid measurement for the change from baseline in percentage of CD4+ lymphocytes producing Th1 cytokine (e.g. INF- $\gamma$ ) in response to any of the 9 peptides in M-001, then this endpoint can be estimated with a precision of at most 2% (1/2 width of the 95% CI).

The trial spans 2 influenza seasons. In each of the 2 cohorts corresponding to season 2018-2019 and 2019-2020, subjects are randomized in a 1:1 ratio to receive two doses (on Day 0 and 22) of either M-001 or saline placebo prior to start of the influenza season.

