## **5.4 Efficacy Endpoints Analysis Methods**

### **5.4.1 Hypothesis**

The hypothesis to be tested is:  $H_0 : VE \leq 40\%$

where VE denotes the vaccine efficacy of M-001 against qRT-PCR- or culture-confirmed influenza in association with protocol-defined ILI over a first season of influenza.

The hypothesis will be rejected and the superiority of M-001 demonstrated if the lower bound of the two-sided 95% CI for VE is  $>40\%$  for the primary per-protocol analysis.

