### **7.2 VE Subgroup Estimates**

In addition to testing the consistency of vaccine efficacy across the subgroups, estimates of VE within the subgroups will be obtained using the Clopper-Pearson method for the binomial proportion from which an exact 95% CI for VE will be derived. These estimates will be obtained on the PP population.

Estimates of VE within the subgroup of Cohort will also be provided for the ITT population. Also, estimates of VE and exact 95% CI by subtype (Type A/H1N1 and Type A/H3N2) or by lineage (Type B/Yamagata) and Type B/Victoria) will be provided if sufficient data is available. Descriptive statistics will be provided for all subgroups including influenza sub-type or lineage.

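### Consistency of VE across subgroups is assessed by a low-powered Breslow-Day p-value, with no interaction estimate or interval for the primary endpoint

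*SAP*

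**What the plan says.** SAP 7.1 names the method: "To assess the consistency of the vaccine efficacy across different subgroups, Breslow-Day test for the homogeneity of the odds ratios will be used". It is applied to the per-protocol population by cohort, age (under 65, 65 and over), sex and flu type (A, B). Age and sex are also tested within each cohort. The results go into Table 14.2.22.1.

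Protocol 11.5.3 uses the test in the same way for age and then adds season: "Breslow-Day test for the homogeneity of the odds ratios will be used to test for a common VE across cohort (flu season").

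Neither document gives a significance level for this test, its power, a margin, or a rule for reading a non-significant result.

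Subgroup estimates are planned as well. SAP 7.2 says: "In addition to testing the consistency of vaccine efficacy across the subgroups, estimates of VE within the subgroups will be obtained", with exact 95% intervals. SAP 5.4.2 provides VE and 95% CI by cohort, by age group and by their combination, in both the PP and ITT sets. Protocol 11.5.3 has VE with intervals by age group and by season. SAP 5.4.2 also fits hazard ratios in the four cohort-by-age strata, as a step towards a combined estimate.

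**The concern.** The null hypothesis of the Breslow-Day test is homogeneity. The test can give evidence against a common VE but cannot establish one. If it is the stated measure of consistency, its usefulness depends on its power, and the trial is sized for a single pooled comparison.

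The useful quantity is an estimate of how much VE differs between subgroups, with its uncertainty. For the primary endpoint that quantity is missing. Two separate VE intervals do not supply it, and judging consistency by whether they overlap is not a valid test of the difference.

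The question matters here. At least half the participants are to be 65 or over, and protocol 2.1.1 describes older people as less responsive to seasonal vaccine. Protocol 11.5.3 notes that circulating strains may change between seasons, while the main analysis in SAP 5.4.2 combines the two cohorts. The SAP does put vaccine-by-cohort and vaccine-by-age interactions in its Poisson model for ILI rates, but has no counterpart for confirmed influenza.

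**Working it through.** **1. The plan's own figure.** SAP 3.4: "The study sample size of 12,000 subjects is based on the lower bound of the two-sided 95% confidence interval" for VE "being above 40% with 80% probability when true VE is 62" per cent. The same section adds "It assumes 1:1 randomization", "a 2.41% attack rate in the study population", up to 10% loss or exclusion, and 182 cases.
- Per-protocol subjects per arm: 12,000 × 0.9 / 2 = 5,400.
- Expected cases, reading 2.41% as the placebo rate: 5,400 × 0.0241 × (1 + 0.38) = 179.6, close to 182.
- Exact conditional power with 182 cases: the probability that a case is in the vaccine arm is 0.38/1.38, and success needs at most 55 vaccine cases. The result is 81.5%, which reproduces the planned 80%.

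**2. Power of the Breslow-Day test for 70% v 50%.** This contrast is an illustration, not a figure from the documents. The placebo attack rate is taken as 2.41% in every subgroup.

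A large-sample approximation uses the log ratio of relative risks, ln(0.5/0.3) = 0.511, with SE = √(sum of 1/cases over the four cells). Power is about Φ(0.511/SE − 1.96) at a two-sided 0.05 level.

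- *Two equal subgroups*, 2,700 per arm each. Placebo cases are 65.1 and 65.1; vaccine cases are 19.5 and 32.5. SE = 0.336, z = 1.52, power 33%.
- *Cohorts*, from 4,055 and about 8,000 enrolled: 4,055 × 0.9 / 2 = 1,825 and 8,000 × 0.9 / 2 = 3,600 per arm. Placebo cases are 44.0 and 86.8.
  - VE 70% in cohort 1 and 50% in cohort 2: vaccine cases 13.2 and 43.4, SE = 0.365, z = 1.40, power 29%.
  - The reverse: vaccine cases 22.0 and 26.0, SE = 0.344, z = 1.49, power 32%.

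Simulating the Breslow-Day test itself (100,000 trials per setting, size 0.050 when VE is equal) agrees:

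| Split | Level 0.05 | Level 0.10 |
|---|---|---|
| Two equal subgroups | 33–34% | 46% |
| Cohorts | 29–33% | 41–45% |
| Age within cohort 1 (about 61 cases) | 14% | 23% |

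If season 1 were milder (placebo rates of 1.5% and 2.87%, assumed), the cohort figure at 0.05 falls to about 21–28%.

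**3. Cases that would be needed.** Scaling the equal-halves case:
- 50% power: 182 × (1.96/1.522)² ≈ 302 cases.
- 80% power: 182 × (2.80/1.522)² ≈ 616 cases.

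**4. What identical estimates would show.** Suppose each of two equal age groups has 25 vaccine and 66 placebo cases, so observed VE is 62% in both and the test gives p = 1.
- SE of the log ratio of relative risks = √(2 × (1/25 + 1/66)) = 0.332.
- 95% CI for the ratio: exp(±1.96 × 0.332) = 0.52 to 1.92.

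Perfect agreement of the estimates would still leave almost a twofold difference in relative risk, in either direction, within the interval.

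**The case against.** Low power for interactions is normal in a trial sized for one hypothesis. SAP 10.1 treats everything beyond the primary endpoint as supportive, and the Breslow-Day result neither gates nor changes the primary conclusion. The subgroup estimates are also substantial: VE with intervals by age, cohort and their combination, in two populations. A marked loss of efficacy in older participants would show in that group's own estimate. All of this stands, and it limits the weight of the point. It does not supply an interval for the difference.

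Three stronger readings are tempting and are not supported.

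- *A reader might infer that a non-significant test will be reported as a common VE.* The protocol's phrasing invites this, but neither document states such a rule.
- *A reader might take the interval of 0.52 to 1.92 to mean that 62% in one age group is compatible with 27% to 80% in the other* (1 − 0.38 × 1.92 and 1 − 0.38 × 0.52). This puts all the uncertainty on one group. The exact 95% CI for a subgroup with 25 of 91 cases in the vaccine arm is about 39% to 77%, which excludes both values. The planned subgroup intervals would show that.
- *A reader might extend the point to a claim of equal VE across vaccine lots.* No current objective makes that claim, and SAP section 11 says no lot consistency analysis will be done.

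The power figures were worked out for age and cohort. Sex is covered only so far as it resembles an equal split. Flu type is not covered, because A and B are outcomes in the same participants rather than separate groups of people.

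**Conclusion.** The point holds as a reporting weakness that is cheap to improve. The stated measure of consistency is a p-value that would miss a 20-point VE difference about two times in three at 0.05, and more than half the time at 0.10. No interval for the difference is planned for the primary endpoint.

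The size rests on about 180–190 cases, equal placebo attack rates across subgroups, an illustrative 70% v 50% contrast, and a test level that the documents leave open. Larger differences are easier to detect: with 182 cases in equal halves, 70% against about 42% would give 50% power, and 70% against about 23% would give 80%.

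The primary analysis is unaffected, and nothing here shows that a planned analysis is invalid.

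**What to change.** In SAP 7.1 and Table 14.2.22.1, make the ratio of relative risks between subgroups, (1 − VE) in one divided by (1 − VE) in the other, with its 95% CI, the measure of consistency for cohort, age and sex. For flu type, give the same ratio with an interval that allows for A and B arising in the same participants, for example by resampling participants. Keep the Breslow-Day p-value as supplementary and state its level. Add to SAP 7.1 and protocol 11.5.3 that p > 0.05 does not establish a common VE.

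The cost is a few lines of wording and an added column. For cohort, age and sex the ratio comes from counts already tabulated; flu type needs a short participant-level calculation. No new data are needed and the primary test does not change. The downside for the sponsor is a less favourable consistency statement, because the intervals will be wide.
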